5.3. Efficacy/Effectiveness Endpoint(s)

Variable	Operational definition
Real-world progression-free survival	
Time in months from the initial endocrine-based therapy to the first progression or censoring date will be calculated.
 
For the purpose of this study, lines of therapy will be defined as the following Progression-based lines, in which a disease progression must occur for a new regimen to be interpreted as a new line of therapy.
 
Event: Any death or disease progression. Disease progression is taken to have occurred when a pathology report or radiological scan indicates disease progression and/or there is a physician progress note consistent with that determination. If patients did not die or have disease progression, they were censored at their last visit date during the study period for patients with only one line of therapy.

Overall survival	
Time in months from the initial endocrine-based therapy to death due to any cause or censoring date will be calculated.
 
Event: Any death recorded in the data extract. Patients who did not die will be censored at the time of data cutoff (assuming this is the last date the SSDI is searched).

Real-world tumor response	
Real-world tumor response (rwTR) will be assessed as best overall response for each regimen received within the initial endocrine-based therapy.
 
Responses will be classified as Complete response (CR); Partial response (PR); Stable disease (SD); Progressive disease (PD); Not evaluable (NE); or Undocumented. The date of the first positive response (CR or PR) and of the best overall response for each regimen will be collected.

Response rate	
The number of patients with complete response or partial response divided by the number of patients with at least one tumor assessment while on the initial endocrine-based therapy.

PFIZER CONFIDENTIAL

Time to first positive response	Months from the start date of the initial endocrine based therapy to the date of the first positive response (CR or PR).
Duration of response	Month from the date of the first positive response (CR or PR) to the date of first PD assessment or death. Patients without a PD assessment or death are censored at the the data cutoff date.
Duration of initial endocrine-based treatment	Months from the start date of the initial endocrine-based therapy to the end date of the initial endocrine-based therapy.

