7. STATISTICAL METHODOLOGY AND STATISTICAL ANALYSES

7.1. Statistical Methods

Mean, standard deviation, median, 1st quartile, 3rd quartile, inter-quartile range, minimum, and maximum will be provided when performing descriptive analysis of continuous data. Numbers and percentages will be provided when performing descriptive analysis of categorical data.

An unadjusted Kaplan Meier curve will be drawn to illustrate each time-to-event outcome. Medians and 95% confidence intervals obtained from the Kaplan-Meier curves will be reported.

All data analysis will be executed using statistical software SAS version 9.4 or later.

PFIZER CONFIDENTIAL

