7.2. Statistical Analyses

Description of demographic, clinical, and treatment characteristics

Descriptive analyses will be conducted to evaluate the demographic, clinical, and treatment characteristics each of the study cohorts. Results will be reported in aggregate. Categorical variables (eg, ECOG performance status) will be reported as frequency and percentage. Continuous variables such as age will be reported as mean, standard deviation, median, 1st quartile, 3rd quartile, inter-quartile range, minimum, and maximum. In the case of missing observations, the number and percentage of missing values will be reported.

[figure not shown]
Description of effectiveness outcomes

For each of the study cohorts, real-world tumor response and response rate will be reported as frequency and percentage. Real-world progression-free survival, overall survival, time to first positive response, duration of response, duration of initial endocrine-based treatment, duration of all treatment, and Duration of follow-up will be assessed with the Kaplan-Meier method with 95% CIs, and summary tables of the number of events and censored patients. No covariates will be included. All missing values are excluded.

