PFIZER CONFIDENTIAL

Progressive Disease	
Not Evaluable	
Undocumented	
Regimenz	
Complete Response	
Partial Response	
Stable Disease	
Progressive Disease	
Not Evaluable	
Undocumented	
...	

Real-world tumor response (rwTR) will be assessed as best overall response for each regimen received within the initial endocrine-based therapy.

Table 8b. Summary of Real-world Tumor Response – *Palbociclib + AI Patients*

Repeat Table 8a for patients receiving Palbociclib with AI as initial endocrine-based therapy.

CCI

Table 9a. Summary of Response Rate – All Eligible Patients

	All Eligible Patients (N=) n (%)
Regimenx	
Regimeny	
Regimenz	
...	

Response rate is calculated as the number of patients with complete response or partial response divided by the number of patients with at least one tumor assessment while on the initial endocrine-based therapy.

Table 9b. Summary of Response Rate – *Palbociclib + AI Patients*

Repeat Table 9a for patients receiving Palbociclib with AI as initial endocrine-based therapy.

CCI

PFIZER CONFIDENTIAL

Table 10a. Time to First Positive Response - All Eligible Patients

	All Eligible Patients (N=)
Number of Positive Response, n (%)	
Number Censored, n (%)	
Kaplan-Meier Estimates of Time to Event (months)	
Median (95% CI)	

Table 10b. Time to First Positive Response - Palbociclib + AI Patients

Repeat Table 10a for patients receiving Palbociclib with AI as initial endocrine-based therapy.

CCI

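### Time to first response: Kaplan-Meier is prescribed with no censoring date for non-responders and no handling of progression or death before response, so the curve depends on an unstated choice

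*SAP*

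**What the plan says.** SAP 5.3 gives the endpoint as "Months from the start date of the initial endocrine based therapy to the date of the first positive response (CR or PR". That row contains no censoring rule and does not mention progression, death or a new line of therapy before response. The row for duration of response, by contrast, does state a rule: "Patients without a PD assessment or death are censored at the the data cutoff date".

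SAP 7.1 says "An unadjusted Kaplan Meier curve will be drawn to illustrate each time-to-event outcome", with medians and 95% confidence intervals. SAP 7.2 lists the endpoint among those ("Real-world progression-free survival, overall survival, time to first positive response, duration of response, duration of initial endocrine-based treatment" and others) that "will be assessed with the Kaplan-Meier method with 95% CIs, and summary tables of the number of events and censored patients". It then adds "No covariates will be included. All missing values are excluded". No competing-risk method is named in the visible text.

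The shell in SAP Appendix 1, "Table 10a. Time to First Positive Response - All Eligible Patients", counts only responses as events ("Number of Positive Response, n"), follows with a row for the number censored, and is headed with the N of the whole cohort. Table 10b and Figures 6a and 6b follow the same pattern.

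Two protocol rules bear on this. Section 9.3.1 closes a regimen at progression and treats anything given afterwards as a new regimen. Section 9.3.2 (item 23) collects responses only to the end of the first progression-based line that contains the qualifying therapy.

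**The concern.** A patient who progresses or dies before responding can never contribute a qualifying response, so progression and death compete with response. Kaplan-Meier has one place for such patients: the censored group. If the censoring date is the date of progression or death, the estimator assumes that they would have gone on to respond at the same rate as those still at risk. One minus Kaplan-Meier then exceeds the proportion who respond by each time, and its median comes too early.

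The date is not stated, so two programmers following this SAP could produce different curves and medians from the same data. Response belongs to primary Objective 2, and Table 10b and Figure 6b present this endpoint for the Palbociclib + AI cohort. In a descriptive study these estimates are the product.

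**Working it through.** **No plan figure to reproduce.** The documents give no response rate and no expected time to response. The nearest stated figure is average follow-up in Protocol 9.5, (50/2) + 8 = 33 months. The calendar dates give 49.87/2 + 8.02 = 32.95, which agrees, so 24 months lies well within follow-up.

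**Inputs from the documents (Protocol section 7).** Hazard of progression or death, λ, assumed constant:
- PFS median 24.5 months: λ = ln 2/24.5 = 0.02829 per month.
- 84.1% progression-free at 12 months: λ = −ln(0.841)/12 = 0.01443 per month, a median of 48.0 months.

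**Assumption.** The response hazard is h per month for 12 months and h/5 after that, with h from 0.030 to 0.075.

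**Reading A: non-responders censored at progression or death.**
- One minus Kaplan-Meier at 24 months = 1 − exp(−12h − 12h/5) = 1 − exp(−14.4h). It does not depend on λ.
- Cumulative incidence at 24 months = h/(h+λ) × [1 − exp(−12(h+λ))] + exp(−12(h+λ)) × (h/5)/(h/5+λ) × [1 − exp(−12(h/5+λ))].

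Example, h = 0.075 and λ = 0.02829: Kaplan-Meier gives 1 − exp(−1.08) = 0.660. Cumulative incidence is 0.7261 × 0.7105 + 0.2895 × 0.3465 × 0.4052 = 0.516 + 0.041 = 0.557.

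24-month results in per cent (excess taken before rounding):

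| h | 1−KM | Cum. inc., median 24.5 | Excess | Cum. inc., median 48.0 | Excess |
|---|---|---|---|---|---|
| 0.030 | 35.1 | 28.8 | 6.3 | 31.7 | 3.4 |
| 0.042 | 45.4 | 37.6 | 7.8 | 41.1 | 4.3 |
| 0.056 | 55.4 | 46.2 | 9.2 | 50.3 | 5.0 |
| 0.075 | 66.0 | 55.7 | 10.4 | 60.4 | 5.7 |

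At 6 months, 1 − exp(−6h) against h/(h+λ) × [1 − exp(−6(h+λ))] gives an excess of 1.3 to 2.7 points (median 24.5) or 0.7 to 1.4 points (median 48.0).

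Medians, like for like, at h = 0.075 and λ = 0.02829: Kaplan-Meier ln 2/0.075 = 9.2 months; cumulative incidence −ln(1 − 0.5/0.7261)/0.10329 = 11.3 months.

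**Sensitivity to the shape of response.** Two other models gave, at 36 months:
- A mixture with 30% to 60% true responders, mean response time 5 months, and non-responders progressing at the PFS median or at half of it: excess about 2 to 10 points.
- A constant response hazard set so that 12-month cumulative incidence is 30% to 60%: excess about 12 to 24 points.

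**Reading B: non-responders, including those who died, kept at risk to data cutoff.** Each patient's time at risk is then fixed by cutoff alone, and Kaplan-Meier returns the cumulative incidence. In the mixture model it gave 30/40/50/60% at 36 months against a true 30/40/50/60%, so the bias is zero. This needs complete response ascertainment to cutoff. With assumed loss to follow-up of 10% or 20% a year, simulation under the piecewise hazards (median 24.5) understated 24-month response by 2 to 3 or 3 to 5 points.

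**Reading C: patients without a response date dropped as missing.** The result is a responders-only time, with a median of about 4.2 months under the mixture assumptions. It carries no information on how many respond.

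**The case against.** The strongest reply is that the SAP nowhere says non-responders are censored at progression or death. Overall survival, duration of response and duration of follow-up are all censored at data cutoff; rwPFS, censored at last visit, is the exception. If cutoff is meant here too, Kaplan-Meier already gives the right curve. This stands. A reader might infer that the SAP treats progression and death as non-informative censoring, or that the result is wrong whichever date is used. The documents support neither: the date is absent, and one plausible choice carries no bias.

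A reader might also set the Kaplan-Meier median (9.2 months in the example) against a responders-only median and call the gap error. Those are different quantities; the proper comparison is 11.3 months. Nor is an unreached cohort median a fault: it is the correct answer when fewer than half respond, and cumulative incidence would show it too.

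The whole-cohort heading of Table 10a is weak evidence on the risk set, because Table 11a carries the same heading although only responders can have a duration of response. The row for censored patients does point to non-responders being included, but the missing-data rule points the other way, so the ambiguity remains.

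Finally, consequences are modest. SAP section 3 sets no hypotheses or decision rules, and Tables 8 and 9 report best response and response rate directly. That limits the harm, but neither table can correct the curve or median in Table 10 and Figure 6.

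**Conclusion.** The concern holds as an incomplete specification with conditional bias. Kaplan-Meier is the only method named, progression and death before response are not handled, and the missing censoring date decides the answer.

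- Censoring at progression or death: 24-month response overstated by about 6 to 10 points (PFS median 24.5 months) or about 3.5 to 6 points (median about 48 months), about 1 to 3 points at 6 months, and a median that is too short.
- At risk to cutoff with complete ascertainment: no bias.
- Missing excluded: a responders-only summary.

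The sizes rest on assumed response hazards and a constant progression hazard. Only the two PFS inputs come from the documents. Other response shapes move the 36-month excess between about 2 and 24 points. The change is worth making, but the impact is limited in a descriptive study that also reports response rate.

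**What to change.** In SAP 5.3, SAP 7.2, Tables 10a/b and Figures 6a/b, replace Kaplan-Meier with the Aalen-Johansen cumulative incidence of first response:
- analyse the full cohort, not responders only;
- count progression or death before response as a competing event;
- censor patients with none of these events at their last visit, as the rwPFS definition does;
- report cumulative incidence with 95% confidence intervals at 6, 12 and 24 months;
- add the median and quartiles of time to response among responders, labelled as such;
- state that having no response is not a missing value for this endpoint.

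Table 10 then needs a row for competing events beside responses and censored patients. The cost is SAP wording and a different SAS option for one endpoint. All the dates needed are already collected under Protocol 9.3.2 and 9.3.3. The curve will look somewhat lower than Kaplan-Meier censored at progression or death, and the cohort median may not be reached.

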16. ECOG/performance status, if available or indication of impaired performance status not otherwise classified as an ECOG rating, at index date (± 60 days). Where available, Karnofsky performance status will be converted to corresponding ECOG score.
17. Comorbidities, indicated as present vs. not indicated as present at index date. The conditions and date of the condition to be assessed will include those assessed as part of the standard Charlson Comorbidity Index. These include myocardial infarction, congestive heart failure, peripheral vascular disease, cerebrovascular accident, hemiplegia, chronic obstructive pulmonary disease, ulcer disease, diabetes, renal disease, connective tissue disease such as rheumatoid arthritis or lupus, Alzheimer's or other dementia, cirrhosis or other serious liver disease, leukemia, lymphoma, metastatic solid tumor (other than breast cancer), and HIV/AIDS.

PFIZER CONFIDENTIAL

18. Other comorbidities of interest, indicated as present vs. not indicated as present at index date: hypertension and hyperlipidemia.
19. Dates of disease progression after index date through the end of the record or the end of the study, whichever occurs first.
20. Documentation of treatment modifications (dose modification, schedule changes, dose delay, hold, or discontinuation) for palbociclib, **CCI** [REDACTED] and reasons for treatment modifications, if applicable, from the index date through the end of the record or the end of the study, whichever occurs first. Date of treatment modification and reason for modification will be collected, if available.
 - Reasons for modification will include: Cost, disease progression, patient refusal/request, toxicity (specify), other (specify), or UD.
21. Oral anti-cancer therapies. This will include all treatments from the index date through the end of the record or the end of the study, whichever occurs first. **CCI** [REDACTED]
22. Documentation of any IV, IM, or subcutaneous anti-cancer therapy not otherwise documented in standard medication tables, including all treatments received from the index date through the end of the record or the end of the study, whichever occurs first. Agent and start and end dates will be collected.

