5. ENDPOINTS AND COVARIATES

- Index date:** Date of A/MBC diagnosis.
- Observation period:** February 3, 2015 through the data cutoff date (end of data curation). Since data curation will start in November 2019, this allows patients to have a potential follow-up of at least 6 months.
- Follow-up:** Patients will be followed from the index date to the data cutoff date, or death, whichever comes first.

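### Duration of response is censored at data cutoff while rwPFS is censored at last visit, so DoR is overstated to the extent that responders' charts end before cutoff

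*SAP*

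**What the plan says.** SAP 5.3 defines three time-to-event outcomes that matter here.

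- **DoR** runs from the first CR or PR "to the date of first PD assessment or death". For everyone else: "Patients without a PD assessment or death are censored at the the data cutoff date".
- **rwPFS** runs from the start of initial endocrine-based therapy. Its event is "Any death or disease progression". Of patients with neither, the SAP says "they were censored at their last visit date during the study period for patients with only one line of therapy".
- **OS** is censored at cutoff, with a reason attached: "assuming this is the last date the SSDI is searched".

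SAP 5 defines follow-up in the same spirit as the DoR rule: "Patients will be followed from the index date to the data cutoff date, or death, whichever comes first". The cutoff is one common date, the end of data curation.

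Protocol 9.3.2, item 19, limits what can be known about progression: "Dates of disease progression after index date through the end of the record or the end of the study, whichever occurs first". Deaths reach further. Protocol 9.3.3, item 4, takes them from the clinical record and from linked SSDI or obituary records.

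SAP 7.2 analyses DoR and rwPFS by Kaplan-Meier with 95% confidence intervals. Nothing in either document explains why the two are censored differently, and no sensitivity analysis is planned.

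**The concern.** A patient may be kept at risk in a Kaplan-Meier analysis only while the event could have been observed. For death, linkage makes cutoff a defensible end of observation, and that is the reason the SAP gives for OS. It does not carry over to progression, which is seen only in the chart. Once a responder's record stops, a later progression cannot enter the data, yet the DoR rule keeps that patient at risk and event-free until cutoff. The curve is then too high, the median too long and its confidence interval shifted upward.

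Death linkage softens this without removing it. The missed progression is replaced either by a later death or by censoring at cutoff.

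The two rules also produce results that cannot both be right. Response comes after the start of therapy, so a patient's DoR should never exceed that patient's rwPFS. Under the present text it can.

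**Working it through.** **1. The plan's own figure.** Protocol 9.5 gives an average potential follow-up of (50/2) + 8 = 33 months. By calendar, 3 Feb 2015 to 1 Apr 2019 is 49.9 months and 1 Apr to 1 Dec 2019 is 8.0 months, so 49.9/2 + 8.0 = 32.95. The figure reproduces. Potential follow-up then spans 8.0 to 8.0 + 49.9 = 57.9 months.

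**2. One patient, no model.** Measure from therapy start: response at R, last visit at L, cutoff at C, no PD or death recorded. Then rwPFS is censored at L and DoR at C − R. DoR exceeds rwPFS whenever C − L > R. Example (R and L assumed): R = 4, L = 24, C = 33. rwPFS = 24 months and DoR = 33 − 4 = 29 months, both censored.

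**3. Effect on the median, no later deaths captured.** Assume exponential time from response to progression with hazard μ, and independent exponential loss with hazard λ. A patient lost before progression never shows an event, so under cutoff censoring the Kaplan-Meier curve estimates

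S*(t) = 1 − [μ/(μ+λ)] · [1 − exp(−(μ+λ)t)],

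and the reported median is t = −ln(1 − 0.5(μ+λ)/μ) / (μ+λ).

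True median 24: μ = ln 2/24 = 0.02888. With 10% lost by 24 months, λ = −ln(0.9)/24 = 0.00439, the ratio μ/(μ+λ) = 0.868, and t = 25.8. With 20%, λ = 0.00930, ratio 0.756, t = 28.3. With 30%, λ = 0.01486, ratio 0.660, t = 32.4. Simulation gives the same values to within 0.1.

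**4. With later deaths captured.** Simulation: 400,000 responders per scenario averaged over 8 seeds, response at 2 to 6 months, potential follow-up uniform on 8.0 to 57.9 months, median survival after progression 12 or 24 months (this gives the ranges). Reported median DoR in months under cutoff censoring:

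| Lost by 24 months | True 24, no deaths captured | True 24, all captured | True 15, none captured | True 15, all captured |
|---|---|---|---|---|
| 10% | 25.8 | 25.0–25.3 | 15.7 | 15.5–15.6 |
| 20% | 28.3 | 26.2–26.9 | 16.5 | 16.0–16.2 |
| 30% | 32.4 | 27.6–29.0 | 17.7 | 16.7–17.1 |

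For a true 24 with 2% or 5% lost, the medians are 24.2 to 24.3 and 24.5 to 24.8.

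**5. Coverage of the 95% CI** (400 responders assumed, 4,000 samples per scenario, log-log interval), at 10/20/30% lost:

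- True 24: 91.0–92.3 / 77.5–84.2 / 52.3–67.2% with all deaths captured; 88.9 / 64.4 / 29.5% with none.
- True 15: 93.1–93.4 / 85.7–88.5 / 70.2–77.5% with all captured; 93.0 / 81.2 / 59.5% with none.

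**6. Share of responders whose DoR exceeds their own rwPFS**, true 24: 5.1–6.7% at 10% lost and 15.2–20.1% at 30% lost. For a true 15: 3.7–5.5% and 11.0–16.7%.

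**7. Different assumptions.** A second simulation took progression medians of 24.5 months (the palbociclib + letrozole PFS cited in Protocol 7) and 18 months, and let 0 to 40% of records end at a random time between response and cutoff. With no early ends, both censoring rules gave the true median (22.9 on the longer scale). With 10 to 40% early ends, cutoff censoring gave 23.7 to 29.6, an excess of 0.8 to 6.7 months. On the shorter scale (true 17.1) it gave 17.7 to 20.9, an excess of 0.6 to 3.8. Last-visit censoring stayed within about 0.4 months of the truth throughout.

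**The case against.** The strongest reply is that the size is unknown and may be small. Loss rate, DoR median, number of responders and death capture are all assumed, and SAP 2.1.2 describes the oncology record as essentially complete. At 2 to 5% loss the shift on a 24-month median is under a month, and at 10% loss with a true median of 15 coverage is still about 93%. This stands as a limit on the size. It does not rescue the rule, because a complete record at the practice does not cover a patient who has moved elsewhere, and Protocol 9.3.2 itself allows for records that end before the study does.

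DoR is also not named in the protocol's objectives, and SAP 3 has no hypotheses or decision rules. That is correct and limits the consequence to interpretation. SAP 7.2.2 does, however, map DoR to Objective 2, and DoR has its own tables and figures.

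Smaller points:

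- The rwPFS rule is restricted to patients with one line of therapy. Because a new line requires a progression, this normally covers every progression-free patient, though the wording should be tidied.
- DoR speaks of a PD assessment and rwPFS of progression by pathology, scan or note. Either way, the event is seen only in the chart.
- Protocol 9.3.2, item 23, stops response abstraction at the end of the first line if that comes sooner. The argument rests on item 19 and does not need item 23.
- Censoring at the last tumor assessment would also be reasonable. Last visit is preferred because it matches rwPFS.

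**Conclusion.** The concern holds. The censoring rule for DoR does not fit the way progression is observed, conflicts with the rule for rwPFS, and lacks the justification the SAP gives for OS. The direction is upward whenever responders' records end before cutoff without PD or death; if none do, the bias is zero. Under the assumptions above (exponential times, loss independent of progression), 10% loss by 24 months adds roughly 1 to 2 months to a true median of 24 and 0.5 to 0.7 to a true median of 15. Thirty percent loss adds about 3.6 to 8.4 and 1.7 to 2.7 months. The inconsistency and its direction are certain; the size in this dataset is not. It should be fixed before the analysis, but it threatens no decision rule.

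**What to change.** In SAP 5.3, replace the DoR censoring sentence with: *Responders with neither PD nor death are censored at their last visit within the study period, as for rwPFS.* Add one rule for both endpoints: *A death found by linkage after the last visit and on or before the data cutoff is an event on the date of death*, and report how many such deaths there are. Cutoff censoring may stay as a sensitivity analysis. OS is unchanged.

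In the simulations of step 4 this brings the median to 23.6–23.9 for a true 24 and 15.1–15.3 for a true 15 (10 to 30% lost, all later deaths captured), with coverage of 94.3 to 95.5%. The small remaining shift, at most about 0.4 months, arises because follow-up extends past the last visit only for those who die. Ignoring those deaths gives 24.0 and 15.0, but departs from the stated event definitions, which include death without restriction.

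The cost is one sentence replaced and one added, slightly less follow-up and a shorter reported median. The rwPFS rule already requires a last visit date. The visible variable lists in Protocol 9.3.2 to 9.3.4 do not name it, so the sponsor should confirm that it is captured. The linked-death rule clarifies an existing rwPFS event and does not redefine it; the sponsor should record that judgement, since Protocol 9.7 calls for an amendment when a primary endpoint definition or its analysis is changed in a major way.

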9.3.4. Derived Variables

Variables suggested to be derived for this study's purpose will be generated by Pfizer analytical team. Final algorithm to derive the variables will be further determined by Pfizer. The suggested variables derived from abstracted and extracted data will include the following:

1. Age at index date, at initiation of the earliest endocrine-based regimen, and at first treatment regimen after the index date.
2. Weighted index of comorbid disease condition. Weighting of comorbid conditions (not including breast cancer) will follow the weighting as specified in the Charlson Comorbidity Index.
3. Start and end dates of anti-cancer treatments from the index date through the end of the record or the end of the study, whichever occurs first.
4. Treatment regimens, derived from oral and infused agents delivered, including start and end dates.
5. Endocrine sensitivity prior to the index date, defined as endocrine sensitive vs. resistant vs. refractory based on adjuvant endocrine therapy experience. Endocrine sensitive: ≥24 months without recurrence/progression after completion of endocrine therapy in the adjuvant setting; Endocrine resistant: recurrence/progression after completion of endocrine therapy, and within 24 months of completion of endocrine therapy; Endocrine refractory: recurrence/progression while on endocrine therapy in the adjuvant setting, defined as occurring while on or within <30 days after discontinuation of endocrine therapy. The 30 day window allows that endocrine therapy may be discontinued because of a perceived progression before that progression is actually documented.
6. Primary endocrine resistance defined as a relapse while on the first 2 years of adjuvant endocrine therapy or disease progression within the first 6 months of first-line endocrine therapy for A/MBC, while on endocrine therapy.

PFIZER CONFIDENTIAL

7. Secondary (acquired) endocrine resistance defined as a relapse while on adjuvant endocrine therapy but after the first 2 years or a relapse within 12 months of completing adjuvant endocrine therapy, or disease progression ≥ 6 months after initiating endocrine therapy for A/MBC, while on endocrine therapy.

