5.2. TREATMENT PATTERN ENDPOINT(S)

Variable	Operational definition
Treatment Regimen Duration	Months from the start date to the end date of a treatment regimen. For ongoing regimen, the end date is the data cutoff date.
Treatment Sequence Duration	Months from the start date of the first treatment regimen to the end date of the last treatment regimen within the same line of therapy. For ongoing regimen, the end date is the data cutoff date. This will be calculated for up to 3 lines of therapy.
The following dosing information will be presented for palbociclib, CCI	
Start dose	Start dose level of palbociclib, CCI
End dose	End dose level of palbociclib, CCI
Duration of Treatment	Months from the start date to the end date of the treatment. For ongoing treatment, the end date is the data cutoff date.
Reason for Discontinuing Treatment	Cost; Disease Progression; Patient Refusal/Request; Toxicity, specify; Death, Other, specify, Undocumented
Time to Dose Discontinuation	Months from the start date to the discontinuation date of the treatment.
Type of Dose Adjustments	Dose Modification; Schedule Changes; Dose Delay; Hold; Discontinuation
Time to First Dose Adjustment	Months from the start date to the first adjustment date of the treatment.

PFIZER CONFIDENTIAL

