Duration of all treatment	Months from the start date of the initial endocrine-based therapy to the end date of the last line of treatment. Patients who are still receiving the initial endocrine-based therapy at the data cutoff date will be censored.
Duration of follow-up	Months from the index date to the date of death, or the data cutoff date, whichever came first. Patients who did not die will be censored at the data cutoff date

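### The censoring rule for Duration of all treatment covers only patients still on the initial therapy; read literally, patients on a later line at cutoff become events and the duration is biased short

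*SAP*

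**What the plan says.** In SAP 5.3, Duration of all treatment is defined as "Months from the start date of the initial endocrine-based therapy to the end date of the last line of treatment". One sentence on censoring follows: "Patients who are still receiving the initial endocrine-based therapy at the data cutoff date will be censored". The row states no event and says nothing about patients receiving a second or later line at cutoff.

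SAP 7.2 lists this endpoint among those that "will be assessed with the Kaplan-Meier method with 95% CIs, and summary tables of the number of events and censored patients". Every analysed patient must therefore be coded as either an event or censored. The same section adds: "No covariates will be included. All missing values are excluded".

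SAP 5.2, on treatment patterns, gives a date for treatment that has not stopped: "For ongoing regimen, the end date is the data cutoff date". It mentions no censoring flag.

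The neighbouring SAP 5.3 row, Duration of initial endocrine-based treatment, reads "Months from the start date of the initial endocrine-based therapy to the end date of the initial endocrine-based therapy". It is also analysed by Kaplan-Meier (Figures 3a/3b) and has no censoring rule.

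Later lines are in scope. The SAP tabulates up to three of them, and the derived variables listed in Protocol 9.3.4 include "Start and end dates of anti-cancer treatments from the index date through the end of the record or the end of the study, whichever occurs". SAP 7.2.2 assigns both durations to Objective 1b.

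**The concern.** The endpoint ends with the last line, but the censoring condition refers to the first therapy. A patient who progressed, started a second line and is still on it at cutoff has not reached the end of treatment, yet does not meet the stated condition for censoring. If the 5.2 convention supplies the missing end date, the cutoff date is recorded as the end of treatment and the patient counts as an event.

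That turns the limit of follow-up into an apparent end of treatment, and only for patients who moved on to further therapy. A Kaplan-Meier estimate that counts incomplete durations as complete is too low. At stake are the curve, the median and the event count for this endpoint.

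**Working it through.** **The plan's own figure.** The documents give no expected value for this duration. The relevant stated figure is average follow-up in Protocol 9.5: 50/2 + 8 = 33 months. It reproduces. It corresponds to uniform entry over 50 months and a cutoff 8 to 58 months after treatment start, which is used below.

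**Inputs from the documents.** First-line median 24.5 months (real-world PFS cited in Protocol section 7, used as a proxy for first-line duration); OS medians 38.5 and 60.1 months (range cited in the same section); 1100 to 1300 patients (1200 used here).

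**Assumptions, not in the documents.** Exponential durations; share *p* going on to later treatment 60%, 80% or 100%; median later-line time 6, 12, 18 or 24 months; first-line medians of 14 and 18 months as alternatives.

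**Central case by formula** (24.5 months, *p* = 0.8, later-line median 12 months). Let λ1 = ln 2/24.5 = 0.02829 and λ2 = ln 2/12 = 0.05776.

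- Mean probability of still being on first line at cutoff: (e^(−8λ1) − e^(−58λ1))/(50λ1) = (0.7975 − 0.1938)/1.4146 = 0.427.
- The same average for λ2: (0.6300 − 0.0351)/2.888 = 0.206.
- Probability of being on a later line at cutoff: *p* × λ1/(λ2 − λ1) × (0.427 − 0.206) = 0.8 × 0.960 × 0.221 = 0.170, or 204 of 1200.
- Event share under the literal rule: 1 − 0.427 = 0.573. With correct censoring: 0.573 − 0.170 = 0.403. So 0.170/0.573 = 30% of the counted events would be patients still on treatment.

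**Effect on the median.** Simulation of 400,000 patients per scenario, comparing censoring on any ongoing line with the literal rule:

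| First-line median, share going on, later-line median | On later line at cutoff | Median, correct | Median, literal | Shortfall |
|---|---|---|---|---|
| 14, 60%, 6 | 8% | 19.7 | 18.6 | 1.1 |
| 24.5, 60%, 6 | 7% | 30.3 | 27.9 | 2.4 |
| 24.5, 80%, 12 | 17% | 39.5 | 32.2 | 7.3 |
| 14, 100%, 18 | 35% | 38.7 | 28.4 | 10.3 |
| 24.5, 100%, 18 | 28% | 51.3 | 35.8 | 15.5 |

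With a later-line median of 24 months, the share on a later line reaches 41% (first line 14, all going on). In the longest case (first line 24.5, all going on), correct censoring does not reach a median while the literal rule gives 37.3 months. In all 36 scenarios the literal rule gave a shorter median, or a median where correct censoring reached none.

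**A second model tied to the cited OS.** Progression is exponential with median 24.5 months; survival after progression is tuned to the OS median.

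- Treatment until 3 months before death: 35.7 falls to 30.6 (OS 38.5); about 57 falls to about 37 (OS 60.1).
- Treatment for half of the time after progression: 31.4 falls to 28.3 (OS 38.5); 43.8 falls to 33.7 (OS 60.1).
- Treatment until 12 months before death, OS 38.5: 30.1 falls to 27.9.

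**The other literal route.** If later-line patients are dropped as having a missing end date, the median is also short: 33.0 against 39.6 months in the central case.

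**The case against.** The SAP never says that later-line patients are events. The row defines no event, names one group to be censored and does not say that it is the only group. The event coding appears only when a convention from SAP 5.2 is carried into 5.3, and a careful programmer might censor these patients anyway. This stands: what can be shown is a gap in the rule and its literal consequence, not how the data will be coded. It does not remove the point, because Kaplan-Meier needs a status for each patient, and the rows for OS, duration of response and duration of follow-up show that this SAP writes its censoring rules out.

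The endpoint is also minor. The study has no hypotheses or decision rules, the protocol objectives do not name this duration, and it has figures but no table shell of its own. This stands too, and it limits the severity.

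The size is assumption-driven. The largest shortfall needs every patient to progress and then be treated without a gap until 3 months before death. The documents support neither, so no single figure should be quoted.

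A reader might infer that the sentence was simply placed in the wrong row, since it fits Duration of initial endocrine-based treatment. It could equally be a slip for patients still on any treatment. The documents do not settle which.

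**Conclusion.** The concern holds as a gap in a written rule. As it stands, nothing censors patients on a second or later line at cutoff, and the literal reading biases Duration of all treatment short. The direction was the same in every scenario. The size is roughly 1 to 20 months on the median. About 7% to 35% of patients are miscoded for later-line medians of 6 to 18 months, and up to 41% at 24 months. Both ranges rest on later-line durations, and on the share of patients treated further, that the documents do not state.

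Three stronger readings are tempting and not supported. The SAP does not state that these patients have finished treatment. That many patients will be on later lines at cutoff is a result of the assumed durations, not a fact in the documents. The study's main effectiveness results are not affected: real-world PFS, OS and response do not use this rule. This should be fixed before the curves are produced, but it does not undermine the study.

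**What to change.** In SAP 5.3, for Duration of all treatment:

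- Define the event as the end of the last line of treatment, with death on treatment counted as the end.
- Censor every patient still receiving any line of anti-cancer therapy at the data cutoff, or at last record if earlier.

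For Duration of initial endocrine-based treatment, add the matching rule: patients still receiving the initial endocrine-based therapy at cutoff, or at last record if earlier, are censored.

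Apply one date convention for ongoing treatment throughout SAP 5.3, and say how it relates to the cutoff-date convention in 5.2.

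The cost is a few sentences and a censoring flag for each of the two endpoints. No new data are needed, since treatment start and end dates are already collected to the end of the record or study. The curves will show more censoring and wider intervals, and the median may not be reached.
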